2.2.3 Safety Analysis Set

The Safety Analysis Set (SAS) includes all randomized patients who received at least one dose of study medication. Patients will be analyzed according to the study treatment they actually received (defined as the study medication administered first) and according to strata information (MDS risk score/IPSS score) recorded in the eCRF.

The FAS is the primary analysis set for the statistical analyses of efficacy. The PPS will be used as the secondary analysis set to perform sensitivity analyses of the primary efficacy endpoint. All analyses of safety are based on the safety analysis set.

2.2.4 Subgroup of interest

The following subgroups will be considered for selected figures and tables:

• IPSS low risk and Asian; IPSS low risk and Non-Asian; IPSS Intermediate 1 risk and Asian; IPSS Intermidiate1 and Non-Asian

For efficacy subgroups, stratification factors i.e., IPSS score (low vs Int-1 risk) and geographical region (Asian countries vs non-Asian Countries) as in the randomization (IVRS) will be used. Asian countries are China, Hong Kong, Malaysia, Thailand, and Taiwan.

2.3 Patient disposition, demographics and other baseline characteristics

A breakdown of reasons will be provided for patients excluded during screening.

The number and percentage of patients randomized will be summarized by region, country, center and treatment arm.

Patient disposition will be summarized for the treatment period, as well as for evaluation and survival follow-up period using the FAS. The disposition table will include:

- Number (%) of treated and untreated patients
- Number (%) of patients who completed the end of treatment
- Number (%) for the primary reason of the end of treatment completion
- Number (%) of patients followed for evaluation period
- Number (%) for the reason of evaluation period completion
- Number (%) of patients entering the survival follow-up
- Number (%) for the primary reason of study evaluation completion
- Number (%) of patients alive at last contact

The number and percentage of patients with any protocol deviation will be tabulated by the deviation type and treatment arm using FAS.

Demographic data and baseline characteristics will be summarized descriptively based on the FAS. Demographic data include age, age group, gender, race, and ethnicity. Age will be presented by region (Asian countries vs non-Asian Countries). Age will be calculated based on patient's first screening date. Baseline characteristics are weight group (<35 kg, 35 - <55 kg, 55 - <75 kg, 75 - <95 kg, $\ge 95 \text{ kg}$), and IPSS score (low vs int-1 risk as in randomization) and will be summarized categorically by treatment arm and for all patients. Height, weight will be summarized continuously using FAS by each treatment arm and for all patients.

Relevant medical histories and current medical condition will be summarized and listed. The summaries will be presented by primary system organ class and preferred term. (Medical history/current medical conditions are coded using MedDRA) using FAS.

Hemoglobin history will be listed using FAS. The listing will include hemoglobin value, unit, sample collection date and study day.

2.4 Treatments (study treatment, compliance)

Duration of study treatment exposure (days), average planned daily dose (mg/kg/day), and average actual daily dose (mg/kg/day) will be summarized by treatment arm and for all

patients. Duration of exposure will be categorized into time intervals. The upper limit of each time interval is calculated based on 364 days (defined as 52 weeks x 7 days) +/- 14 days for each year (< 379 days; 379- <743 days; 743- <1107 days; 1107- <1471 days, 1471- <1835 days; >=1835 days). Frequency counts and percentages will be presented for the number of patients in each interval. Total patient years will also be reported.

Average (actual) and planned dose (mg/kg/day) will be summarized similarly.

The frequency in changes of planned dose (reductions and increases), overall and by reason for change, will be summarized. Reasons for interruptions (actual dose zero) will also be summarized by treatment arm and for all patients.

Listings of all doses of the study treatment along with dose change and dose interruption reasons will be produced.

The percentage of total dose taken will be used as an assessment of a patient's compliance and calculated as the amount of medication (deferasirox/placebo) taken versus the planned amount of study medication. Percentage of total dose taken will be summarized by treatment arm and for all patients.

The Safety Analysis Set will be used for all summaries and listings of study treatment.

2.4.1 Duration of exposure

The following algorithm will be used to calculate the duration of study treatment exposure for patients who took at least one dose of any study treatment (DFX or placebo):

Duration of exposure (days) = $[(date \ of \ last \ administration \ of \ study \ treatment) - (date \ of \ first \ administration \ of \ study \ treatment) + 1]$

The date of last administration of study treatment (treatment component) is taken from the DAR eCRF. The calculation of 'duration of exposure 'does not consider the potential lagging effect' from the last dose.

Duration includes the periods of temporary interruption of the study treatment for any reason. 'Date of first administration of study treatment 'and 'date of last administration of study treatment' are defined in Section 2.1.2.2 and Section 2.1.2.3 respectively.

Exposure duration excluding interruption will also be calculated using the following algorithms:

Duration of exposure excluding interruption = duration of exposure (days) – number of days drug being interrupted (0 dose)

2.4.2 Cumulative dose

Cumulative dose (mg/kg) is defined as sum over daily doses of all days between first and last dose. For patients who did not take any drug, the cumulative dose is by definition equal to zero. In this study, dose is weight adjusted.

The **planned cumulative dose** for a study treatment component refers to the total planned dose as per the protocol up to the last date of investigational drug administration. The **actual cumulative dose** refers to the total actual dose administered, over the duration for which the subject is on the study treatment as documented in the Dose Administration eCRF.

2.4.3 Average planned and actual dose

Average planned and actual dose are defined by the following algorithm:

Average planned dose (mg/kg/day) = [Cumulative planned dose during the time of exposure]/Duration of exposure (days)

Average actual dose (mg/kg/day) = [Cumulative actual dose during the time of exposure]/Duration of exposure (days)

2.4.4 Percent dose taken

Percent dose taken = 100 times ratio of average (actual) dose and average planned dose

2.4.5 Concomitant, prior and post therapies

Concomitant therapy is defined as all interventions (therapeutic treatments and procedures) besides the study treatment that were administered to a subject preceding or coinciding with the study assessment period.

Concomitant medications entered into the database will be coded using the World Health Organization (WHO) Drug Reference List to allow for categorization by preferred term. In addition to categorizing medication data by preferred term, drugs are classified according to their ATC classification in order to present and compare how they are being utilized.

Concomitant medications and significant non-drug therapies taken concurrently with the study drug(s) will be listed and summarized categorically by Anatomical Therapeutic Chemical (ATC) class and preferred term for each treatment arm. These summaries will include medications starting on or after the start of study treatment or medications starting prior to the start of study treatment and continuing after the start of study treatment.

Any prior concomitant medications or significant non-drug therapies starting and ending prior to the start of study treatment will be listed separately.

Patients discontinue from study drug may receive post-treatment chelation therapy. Statistical analysis for post-treatment chelation therapy will be outlined in Section 2.4.5.2.

2.4.5.1 Prior chelation therapy

History of iron chelation therapy and blood transfusions will be collected retrospectively six months prior to study entry.

Duration of iron chelation prior to study entry will be categorized into time intervals (< 1, 1-<3, 3-<6 months of cumulative therapy). Frequency counts and percentages will be presented for the number of patients in each interval. The number of patients who received different prior iron chelators will also be summarized by treatment and for all patients.

Prior chelation therapy will be listed using FAS.

2.4.5.2 Chelation therapy after discontinuation of study treatment

The number of patients chelated since discontinuation of study drug will be summarized and categorized as reported within 28 days since discontinuation or later. In the summary table, deferoxamine mesilate will be displayed as "deferoxamine".

Chelation therapy after discontinuation of study treatment will be listed using the FAS.

2.4.5.3 Blood transfusion

The number of blood transfusions during the study will be summarized by type of transfusion, e.g., packed red blood cells (PRBC), platelets, or whole blood. Statistics on average hematocrit per patient, total number of units transfused during the study, and total number of transfusion received six months prior to study start will also be provided using the FAS. To calculate the total volume, only PRBC and whole blood will be taken into account. 450 mL of whole blood is assumed to correspond to 185 mL of PRBC and will be considered as one unit.

Data on blood transfusions will be presented in a listing using FAS.

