#### 6.7.4 Other concomitant medications

The investigator should instruct the patient to notify the study site about any new medications he/she takes after the start of the study drug. All medications (other than study drug) and significant non-drug therapies (including physical therapy and blood transfusions) administered after the patient starts treatment with study drug must be listed on the appropriate eCRF page.

The treatment of concomitant medical conditions with non-investigational medications during the study may be continued with the exception of other chelating agents.

The following concomitant medications may be permitted for use while patient is on study and information outlining start date(s) and end date(s) of each medication taken must be recorded on the appropriate eCRF:

- Erythropoietin (growth factor)
- G-CSF (growth factor)
- GM-CSF (growth factor)
- Azacitidine
- Thalidomide
- Arsenic trioxide
- Lenalidomide
- Decitabine
- Cyclosporine A
- Vitamin C supplements (≤ 200 mg/day)

Any investigational drug other than study medication is NOT allowed during the study. After permanent discontinuation of the randomized study medication, the use of commercially available iron chelation therapies is allowed.

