Week 	-5 1	to -	Day 1	2	4	8	12	16	20	24	28	32	36	40	44	48	52	56 368	372				

- 15. Transfusions may be administered as necessary throughout the study and number and volume (ml) of PRBC and platelets administered are to be recorded in eCRF.
- 16. Required for Females of child bearing potential only.
- 17. A 2 hour fasting Glucose Tolerance test will be done at screening and annually (Weeks 52, 104, 156, 208, 260, 312, 364) and at study treatment discontinuation. Patients should fast for at least 5 hours prior to the test being drawn. Should a patient have a documented diagnosis of diabetes requiring treatment with medication, the Glucose Tolerance Test is not mandatory and is up to the Investigator's discretion. The Glucose Tolerance Test should be performed annually during the Evaluation Period.
- 18. Visit Windows: The following visit windows are permitted: ±3 days Weeks 2 & 4; ±7 days for every monthly visit (Weeks 8, 12, 16, 20 through EOT); ±2 weeks for Evaluation and Survival Follow-Up visits

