2.1.2.7 Month

A month will be calculated as (365.25 / 12) = 30.4375 days. If duration is to be reported in months, duration in days will be divided by 30.4375.

2.1.2.8 **Baseline**

Unless otherwise specified below, for *efficacy evaluations*, the baseline value is defined as the last available measurement before or on the day of randomization (including results from unscheduled visits analyzed by the central laboratory). It is assumed that assessments scheduled for Visit 3 – the randomization visit – were done prior to randomization in order to be interpreted as *prior to or on the day of randomization* (e.g. physical examination, chest x-ray). If an assessment is done at both screening visits, Visit 1 and Visit 2, the value of Visit 2 is considered the baseline value.

Differing definitions for baseline values were specified for the following assessments or parameters:

• Serum creatinine, creatinine clearance, ALT/AST, serum ferritin, total and direct bilirubin: the baseline value is defined as the mean of the Visit 1 and Visit 2 values. If additional measurements analyzed by the central laboratory are available from

unscheduled visits in the screening period, they will be included in the average. Only the central lab values between -35 days and day 1 from randomization date will be considered to determine baseline.

• Transfusion history: data of platelet and PRBC transfusion records in the 6-month period prior to study start (randomization) will be used to establish baseline transfusion frequency and hematologic counts.

For *safety evaluations* (e.g., laboratory and vital signs etc.), the last available assessment before or on the date of start of study treatment is taken as the 'baseline' assessment.

If patients have no value as defined above, the baseline result will be missing.

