2.1.2.9 On-treatment assessment/event and observation periods

The overall observation period will be divided into three mutually exclusive segments:

- 1. *pre-treatment period*: before the first administration of study treatment
- 2. *on-treatment period*: from date of first administration of study treatment to 28 days after date of last actual administration of any study treatment (including start and stop date)
- 3. *post-treatment period*: starts on day 28+1 after last administration of study treatment.

Per study design, there will be two additional observation periods:

- 4. *study evaluation period:* starts on day 29 after last administration of study treatment until study evaluation completion period (visit frequency every three months)
- 5. **survival follow-up period:** starts after study evaluation completion visit until LPFV plus three years or death. If a patient declines to participate in the evaluation period, the survival follow-up period will start on day 29 after last administration of study treatment until LPFV plus three years or death (visit frequency is every 6 months).

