2.7.1.1 Hematologic improvement

Hematologic improvement (HI) in terms of erythroid response during treatment will be assessed based on International Working Group (IWG) criteria (Cheson 2006).

The variable used in the analysis of HI will be the proportion of patients who satisfy the erythroid response criteria; namely,

• Hemoglobin increased $\geq 1.5 \text{ g/dL}$

OR

Reduction of ≥ 4 units of RBC transfusions over 8 weeks, in comparison to 8 weeks' pretreatment values, and lasting at least 8 weeks.

For purposes of calculating the reduction in transfusions component of this endpoint, a transfusion unit is defined as 185 mL of PRBC (Cohen Glimm Porter 2008). According to IWG criteria, HI is measured in patients with pre-treatment hemoglobin levels of less than 11 g/dL or RBC transfusion dependence. The definition of transfusion dependency is based on IWG criteria (Cheson 2006). All patients included in this study are transfusion dependent. In order to measure hemoglobin increase, the last hemoglobin value measured prior to randomization will be used as the pretreated value. If 2 pre-treated (prior randomization) hemoglobin values are available and each is at least 7 days after any transfusion, an average of the 2 values will be used to determine the pre-treatment hemoglobin level. All RBC transfusions regardless of pre-transfusion hemoglobin level, will count in the RBC transfusion response criteria. If any pre-treatment hemoglobin value or transfusion history over 8-week period cannot be determined, they will not be a part of risk set and will not be included in the percentage calculation.

All episodes of HI in the patient will be considered.

The percentage of responders will be summarized for the two treatment groups and $100(1-\alpha)\%$ confidence intervals with α of 0.05 will be provided. The 95% confidence limits for the difference of two proportions will be derived by the Wilson score test (see Section 5.5.3).

Overall survival

Overall survival (OS) will be evaluated in patients treated with either deferasirox or placebo. The variable used in the analysis of overall survival is time to death measured in days. It is defined as date of death (irrespective of cause) minus date of randomization plus 1.

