2.7.1.8 Infections

Infections requiring intravenous antimicrobials during the treatment period (until the 28 day follow-up visit) will be evaluated separately for each treatment group.

Definitions:

- Infections will be determined from the reported adverse events with system organ class "Infections and infestations" and action taken "Concomitant medication taken".
- Antimicrobial therapy will be determined from the reported concomitant medications for patients who had an infection AE. The medications will be based on a pre-specified list of WHO low level ATC codes. The route of administration needs to be specified as "intravenous (i.v.)".
- Identified events will be combined with medications (of the same patient) based on the following criterion: start date of medication ≥ start date of AE and start date of medication ≤ minimum (start date of AE + 1, end date of AE).

The total number of infections requiring intravenous antimicrobials will be counted and summarized per treatment group. For this number, one patient can contribute more than one infection event. To account for different lengths of observation time in the two groups, the rate of infections will be calculated with the number of recorded infections treated with intravenous antimicrobials divided by the total number of patient-years of follow-up. The relative risk of infection will be calculated as the rate of infection in the treatment group compared with the rate in the placebo group.

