5.5.4 Treatment switching to new chelator(s)

If there is a high differential in the proportion of patients (more than 10%) of switching to new chelation therapy prior to experiencing event-free survival event in the placebo arm compared to Deferesirox arm, then a set of additional analyses may be performed: descriptive summaries of a selected set of baseline and disease characteristics and a model-based analysis such as IPCW or RPSFT to account for potential confounding of new chelation therapy.

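### SAP 2.4.5.3 reports transfusions as raw totals in mixed measures with no time denominator, so pre-study and on-study figures cannot be compared, and arm totals only if observation time is equal

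*SAP*

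**What the plan says.** SAP 2.4.5.3 (Blood transfusion) sits in the section on concomitant, prior and post therapies. On the Full Analysis Set it plans the number of on-study transfusions by product type, and then average hematocrit per patient, "total number of units transfused during the study, and total number of transfusion received six months prior to study start". It counts 185 mL of packed red cells, or 450 mL of whole blood, as one unit. It states no rate and no person-time, and does not name the observation period meant.

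Other places bear on this:

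- **Baseline.** SAP 2.1.2.8 says the six-month platelet and red-cell records "will be used to establish baseline transfusion frequency and hematologic counts". The protocol's transfusion subsection under 7.5.5 gives the same purpose.
- **Periods.** SAP 2.1.2.9 divides observation into pre-, on- and post-treatment segments, then adds: "Per study design, there will be two additional observation periods" (study evaluation and survival follow-up).
- **Collection.** Protocol Table 7-1 marks transfusions from Visit 3 to Study Evaluation Completion (778), and not in survival follow-up. Footnote 15 says that "number and volume (ml) of PRBC and platelets administered are to be recorded in eCRF".
- **Infections.** SAP 2.7.1.8 does use a time denominator: "To account for different lengths of observation time in the two groups, the rate of infections will be calculated".
- **Erythroid response.** SAP 2.7.1.1 matches its windows, requiring a reduction of at least 4 "units of RBC transfusions over 8 weeks, in comparison to 8 weeks' pretreatment values".

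**The concern.** A total is a rate multiplied by the time observed. The pre-study time is the same for everyone, but the on-study time is not. Entry was staggered over several years, the study ends three years after the last enrollment (protocol section 4), patients die or leave, and they may decline the evaluation period after stopping drug. The on-study total therefore mixes transfusion need with length of observation.

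The plan sets up a baseline transfusion frequency but plans no on-study frequency to compare with it. It also changes measure between the periods, from transfusions to units. A reader who sets the two figures side by side, or one arm's total beside the other's, has no means in that table of telling a change in need from a difference in time.

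What is at stake is the reading of a descriptive table on a clinically relevant quantity. Erythroid response will not fill the gap, because it registers only improvement.

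**Working it through.** The plan states no figure here to reproduce, so the check is arithmetic on its rule.

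**Inputs**

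- Minimum anticipated need: 8 units per year (protocol 5.1), used as an illustrative constant rate.
- Pre-study window: 6 months (SAP 2.1.2.8 and 2.4.5.3).
- Enrollment: 5 randomized by 12 November 2010 (Amendment 2), 124 enrolled by July 2013 (Amendment 4), 210 planned by December 2014.
- Study end: taken as 31 December 2017, three years after planned last enrollment (assumption).

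**1. Before against during, need unchanged.** Total = rate × time. Pre-study total = 8 × 0.5 = 4 units.

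| Time observed on study | Units on study | Ratio to pre-study total | Units per month |
|---|---|---|---|
| 3 months | 2 | 0.5 | 0.67 |
| 6 months | 4 | 1.0 | 0.67 |
| 12 months | 8 | 2.0 | 0.67 |
| 3.0 years | 24 | 6.0 | 0.67 |
| 4.42 years | 35.4 | 8.8 | 0.67 |
| 372 weeks (7.13 years) | 57.0 | 14.3 | 0.67 |

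The raw ratio runs from 0.5 to 14.3 with no change in need. The monthly rate is constant and equals the pre-study rate, 4/6 = 0.67.

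**2. How far planned time varies.** To the assumed study end there are 7.13 years from 12 November 2010, 4.42 from 31 July 2013 and 3.00 from 31 December 2014. Planned maximum time is then:

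- 7.1 years or more for 5 patients (5/210 = 2%);
- 4.4 to 7.1 years for 124 − 5 = 119 patients (57%);
- 3.0 to 4.4 years for 210 − 124 = 86 patients (41%).

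Deaths and early exits shorten these.

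**3. A rise that looks like a fall.** Need rises 50%, to 12 units per year, and the patient leaves at 3 months. On-study total = 12 × 0.25 = 3 units, against 4 before. As rates it is 3/3 = 1.00 against 4/6 = 0.67 units per month, a ratio of 1.5.

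**4. Mixed measures.** Suppose 1, 2 or 3 units per transfusion (assumed). Four pre-study units are then 4, 2 or 1.3 transfusions. Eight on-study units in a year are 2, 4 or 6 times that count, again with need unchanged.

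**5. Between arms.** Per patient, raw ratio = rate ratio × follow-up ratio (deferasirox/placebo). The follow-up ratios are assumed.

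| Follow-up ratio | Raw ratio, true rate ratio 1.0 | Raw ratio, true rate ratio 1.2 |
|---|---|---|
| 0.80 | 0.80 | 0.96 |
| 0.90 | 0.90 | 1.08 |
| 1.00 | 1.00 | 1.20 |
| 1.10 | 1.10 | 1.32 |

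Arm grand totals would also differ about twofold under 2:1 allocation: at 8 units per year for 2 years, 140 patients give 2240 units and 70 give 1120. Per-patient statistics remove that factor but not the time factor.

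**6. Does erythroid response cover it?** A fall of 4 units per 8 weeks needs at least 4 × 52/8 = 26 units per year at baseline. At 8 units per year a patient receives 8 × 8/52 = 1.2 units per 8 weeks and cannot meet the transfusion criterion. A rise is not counted at any baseline.

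**The case against.** The strongest reply is that this is a treatment description, not an efficacy analysis. The section plans no contrast, test or interval. Amendment 4 moved transfusion frequency and amount into the hematologic improvement endpoint, which uses matched windows. Infections are divided by time because their rate is a named secondary endpoint, and a transfusion rate is not. All of that stands, and it limits the weight of the point. It does not make the totals interpretable, and the improvement endpoint looks in one direction only.

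Second, SAP 2.4 already reports duration of exposure by arm and total patient-years, and SAP 2.3 reports disposition for each period, so a large imbalance would be visible. That also stands, but the exposure figures cover time on study drug in the Safety Set, while the transfusion totals cover the study in the Full Analysis Set. They are not the matching denominator.

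Third, Table 7-1 largely settles the on-study window, since collection runs from Visit 3 to 778. This is fair, though the SAP should say so.

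Fourth, randomization balances potential follow-up in expectation, so staggered entry does not bias the arm comparison. This is correct: step 2 bears only on the before/during comparison.

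Finally, table shells or programming notes outside these documents might add a rate. That cannot be excluded, but the SAP text does not ask for one.

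**Conclusion.** The point holds for this table. By its stated rule, the pre-study and on-study figures are not comparable, because they differ in time and in measure. Arm totals are comparable only if observation time per patient is equal. The before/during distortion needs no assumption about the arms; its size (0.5 to 14.3 times in step 1) rests on an illustrative constant 8 units per year. The between-arm figures are conditional on assumed follow-up ratios. This is a cheap improvement to a descriptive table, and no primary or secondary endpoint changes.

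A reader might infer more than the documents support:

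- **That the arms will in fact be observed for different times.** Follow-up by arm is not given. SAP 5.5.4, on a "high differential in the proportion of patients (more than 10%) of switching to new chelation therapy", is conditional and concerns chelator use, not observation time. Transfusions are still recorded at evaluation visits after study drug stops.
- **That cytopenia makes the on-treatment window end informatively.** Protocol 6.7.1.10 speaks of interruption, with possible reintroduction. An interruption does not end that window.
- **That no other output could show rising need.** Transfusions count as non-drug therapies (protocol 6.7.4) and are summarized under SAP 2.4.5. Adverse events requiring additional therapy, anemia and hemoglobin shifts are also tabulated (SAP 2.8 to 2.8.3). These may hint at a rise, but none gives a transfusion rate.

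**What to change.** In SAP 2.4.5.3 keep the raw totals, use units in both periods, and add red-cell-equivalent units (by the conversion already stated) per patient-month, by arm. Report arm total units divided by arm total patient-months, plus the per-patient median and quartiles, for:

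- **(a)** the six months before randomization, from the transfusion records that the protocol already requires;
- **(b)** randomization to the earliest of: the last visit at which transfusions were collected (778, or 777 if the evaluation period is declined), death, or the last visit before loss to follow-up;
- **(c)** optionally, in treated patients only, first dose to the earliest of visit 777, death or loss.

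The end date must not be the date of the last transfusion. State the number of patients with usable pre-study volumes, since SAP 2.7.1.1 allows that even an 8-week history may be undeterminable. An exploratory rate ratio with a 95% confidence interval, from an overdispersed count model with log time as offset and the pre-study rate as covariate, is optional.

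The cost is SAP wording and a few table rows. No new collection should be needed: on-study number and volume are recorded, and six-month records are required. That those records hold volumes for the full six months is an assumption to confirm.
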